1.2. Study Design

This is a prospective, randomized, double-blind (DB), placebo-controlled, multicenter, interventional study in men and women ≥ 18 and ≤ 75 years of age with SAPH. Study intervention will be up-titrated to allow each participant to reach their individual maximum tolerated dose (iMTD), in the range of 200 μg to 1,600 μg twice daily. For participants with moderate hepatic impairment (Child-Pugh Class B) or who are concomitantly taking a moderate cytochrome P450 (CYP)2C8 inhibitor(s) the dosing frequency is once daily.

[figure not shown]
The study starts with the first Informed Consent Form (ICF) signed by the first participant and ends with the last safety follow-up telephone call (TC) or visit of the last participant. The study comprises the following periods:

- A screening period of up to 30 days: starts with the signature of the ICF and ends with the participant's randomization at Visit 2, Day 1. The screening period should last at least 14 days to allow collection of baseline data for daily life physical activity (DLPA), sleep parameters, and Pulmonary Arterial Hypertension-Symptoms and Impact (PAH-SYMPACTTM).
- Intervention and observation periods:
 - A main observation period (MOP) that starts with the participants' randomization at Visit 2, Day 1 and with a titration phase of up to 12 weeks. Participants receive double-blind study intervention (selexipag or placebo) during this period. It ends on the day of the EOMOP visit. The EOMOP visit is the data cut-off for the primary efficacy and safety analyses. The EOMOP visit for all participants is planned at 39 Weeks ± 1 month after randomization of the last participant. The duration of the MOP will be different for each individual participant and will depend on the time of each participant's individual date of randomization.
 - Participants who prematurely discontinue study intervention before the EOMOP visit will continue to perform visits and assessments as scheduled until the EOMOP visit.
 - For participants who prematurely discontinue study intervention before the EOMOP visit and who disagree to perform visits and assessments as scheduled until the EOMOP visit, long-term follow-up information regarding their survival status will be collected yearly until death or the time of EOMOP.

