5.1.4. Imputation Rules for Missing Date/Time of Onset/Resolution

Partial AE onset dates will be imputed as follows:

- If the onset date of an adverse event is missing day only, it will be set to:
 - First day of the month that the AE occurred, if month/year of the onset of AE is different than the month/year of the first dose of study treatment.
 - The day of first dose of study treatment, if the month/year of the onset of AE is the same as month/year of the first dose of study treatment and month/year of the AE resolution date is different
 - The day of first dose of study treatment or day of AE resolution date, whichever is earliest, if month/year of the onset of AE and month/year of the first dose of study treatment date and month/year of the AE resolution date are same
- If the onset date of an adverse event is missing both day and month, it will be set to the earliest of:
 - January 1 of the year of onset, as long as this date is on or after the first dose of study treatment
 - Month and day of the first dose of study treatment, if this date is the same year that the AE occurred
 - Last day of the year if the year of the AE onset is prior to the year of the first dose of study treatment,
 - The AE resolution date.
- Completely missing onset dates will not be imputed, but the event will be assumed to be treatment emergent unless otherwise indicated.

Partial AE resolution dates not marked as ongoing will be imputed as follows:

- If the resolution date of an adverse event is missing day only, it will be set to the earliest of the last day of the month of occurrence of resolution or the day of the date of death, if the death occurred in that month.
- If the resolution date of an adverse event is missing both day and month, it will be set to the earliest of December 31 of the year or the day and month of the date of death, if the death occurred in that year.
- Completely missing resolution dates will not be imputed.

Concomitant therapy start dates will be imputed as follows:

- If the start date is missing day only, it will be set to first day of the month.
- If the start date has the year, but is missing the month, it will be set to January 1.
- If the start date is completely missing, it will not be imputed

Concomitant therapy end dates will be imputed as follows:

- If the end date is missing day only, it will be set to last day of the month.

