5.6.2. Adverse Events

The verbatim terms used in the CRF by investigators to identify adverse events will be coded using the Medical Dictionary for Regulatory Activities (MedDRA). Any AE occurring at or after the initial administration of study intervention through the day of last dose plus 3 days is considered to be treatment emergent. If the event occurs on the day of the initial administration of study intervention, and either event time or time of administration are missing, then the event will be

assumed to be treatment emergent. If the event date is recorded as partial or completely missing, then the event will be considered to be treatment emergent unless it is known to be prior to the first administration of study intervention based on partial onset date or resolution date. All reported treatment-emergent adverse events will be included in the analysis. For each adverse event, the number and percentage of participants who experience at least 1 occurrence of the given event will be summarized by intervention group.

Summaries will be displayed by treatment (selexipag or placebo) and will include all events up to 3 days after the last dose of study drug or EOS, whichever occurs first.

Summary tables will be provided for treatment-emergent adverse events:

- AEs
- Serious AEs (SAEs)
- AEs leading to discontinuation of study intervention
- AEs by severity
- AEs by relationship to study intervention
- All SAEs up to 30 days after the last study treatment

In addition to the summary tables, listings will be provided for participants who:

- Had AEs
- Had SAEs
- Had AEs leading to discontinuation of study intervention
- Had AEs of COVID-19
- AEs of special interest ([Appendix 8](#))

Deaths will be displayed by actual intervention received. Frequencies for the following parameters will be included in the summary table:

- Number of participants who died
- Cause of death
- Relationship to study intervention (yes/no)

A listing of participants who died will be provided.

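### The partial-date rule in SAP 5.6.2 has no upper bound, so an adverse event dated wholly after last dose + 3 days can be flagged treatment-emergent, against the window and summary limit in the same section

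*SAP*

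**What the plan says.** SAP 5.6.2 makes four statements that bear on this point.

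- The window: an event from first administration "through the day of last dose plus 3 days is considered to be treatment emergent".
- Incomplete dates: an event whose date is partial or wholly missing is "considered to be treatment emergent unless it is known to be prior to the first administration of study intervention based on partial onset date", or on the resolution date. That is the only exception.
- Inclusion: "All reported treatment-emergent adverse events will be included in the analysis".
- The limit on summaries, in the next paragraph: they "will include all events up to 3 days after the last dose of study drug or EOS, whichever occurs first".

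SAP 5.1.4 supplies imputed onset dates. If only the day is missing, the imputed date is the "First day of the month that the AE occurred, if month/year of the onset of AE is different" from that of first dose. If the day and month are both missing, it is the earliest of several candidates, including 1 January of the onset year where that is not before first dose. Completely missing onset dates are not imputed; those events are presumed treatment-emergent unless something indicates otherwise.

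Off-drug events can reach the database. SAP 1.2 says: "Participants who prematurely discontinue study intervention before the EOMOP visit will continue to perform visits and assessments as scheduled until the EOMOP visit". The protocol's Schedule of Activities collects adverse events up to the EOS visit, which for these participants can be the EOMOP visit.

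**The concern.** The window has two ends, but the exception for incomplete dates protects only the first. Presuming an event treatment-emergent when its date leaves doubt is ordinary practice. This rule goes further: it also catches events about which there is no doubt, because every day compatible with the recorded month or year falls after the window has closed.

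Two programmers could follow the SAP faithfully and build different tables. One sets the flag from the partial-date sentence and includes every flagged event. The other applies the summary limit to the imputed onset date. Intervention-emergent adverse events are a named safety endpoint, and efficacy is only listed in this shortened report, so the definition behind the by-arm adverse event tables should be unambiguous.

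**Working it through.** The plan states no figure to reproduce here, so the check runs the rules on example dates.

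**Inputs.** The window, partial-date rule and summary limit come from SAP 5.6.2, and the imputation from SAP 5.1.4. The dates are assumed for illustration: first dose 10 Mar 2021, last dose 15 Jun 2021. The window ends on 15 Jun + 3 days = 18 Jun 2021.

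**Rules compared.**

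1. Literal partial-date rule: treatment-emergent unless the latest possible onset, or the resolution date, is before first dose.
2. Imputed date against the limit: inside if first dose ≤ imputed onset ≤ last dose + 3 days.
3. Rule with an upper bound: treatment-emergent under rule 1, and the earliest possible onset ≤ last dose + 3 days.

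| Recorded onset | Possible days from last dose | Imputed onset (5.1.4) | Rule 1 | Rule 2 | Rule 3 |
|---|---|---|---|---|---|
| Feb 2021 | −134 to −107 | 1 Feb 2021 | no | outside | no |
| Jun 2021 | −14 to 15 | 1 Jun 2021 | yes | inside | yes |
| 2021, no month | −165 to 199 | 10 Mar 2021 | yes | inside | yes |
| Nov 2021 | 139 to 168 | 1 Nov 2021 | **yes** | **outside** | no |
| 2022, no month | 200 to 564 | 1 Jan 2022 | **yes** | **outside** | no |

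Rules 1 and 2 disagree only in the last two rows, where the whole range of possible dates lies after the window. Rule 3 changes those two rows and no others. Events that could have begun on drug (rows 2 and 3) stay treatment-emergent.

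**Boundary cases.** With a last dose on 29 Jun 2021 and onset recorded as July 2021, the imputed date of 1 Jul is within the window ending 2 Jul, although the true gap is anywhere from 2 to 32 days. With a last dose on 30 Dec 2021 and onset recorded as 2022, the imputed date of 1 Jan is within the window ending 2 Jan, and the true gap is 2 to 366 days. Both stay treatment-emergent under all three rules. These dates are truly ambiguous, and the convention resolves them towards inclusion.

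**Effect of one event.** One affected participant moves an arm's incidence for a term by 1/n. At the planned 37 per arm that is 1/37 = 2.7 percentage points. At an assumed 20 or 10 per arm after early termination it is 1/20 = 5 or 1/10 = 10 points. This holds only if the participant has no other treatment-emergent occurrence of that term, because the tables count participants with at least one. It illustrates the scale and does not estimate the impact.

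**The case against.** The strongest reply is that SAP 5.6.2 already contains an upper limit. The summaries stop at last dose + 3 days or EOS, and SAP 5.1.4 gives every partial onset date a value against which that limit can be tested. Applied together, they exclude the November 2021 and 2022 events. This stands. A reader might infer from the partial-date sentence alone that late off-drug events will be counted as on-treatment; the documents do not support that. A reader might also infer that 5.1.4 classifies these events the opposite way. It does not: for partial dates it only imputes a value, and its one statement on treatment emergence concerns completely missing dates, where it agrees with 5.6.2.

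The reply does not remove the contradiction. The limit governs what the summaries show and leaves the flag unchanged. The inclusion sentence puts every flagged event into the analysis, with no order of precedence. Nothing says that imputed dates are used to apply the limit. Nor is the 3-day limit uniform, since the tables listed under treatment-emergent events include one of SAEs up to 30 days after last treatment.

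The practical effect may well be slight. It needs an incomplete date and an onset off drug. Participants who decline further visits contribute only survival data, EOMOP is now premature, and individual listings would expose a misflagged event. All of this stands.

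**Conclusion.** Wrong as written. The partial-date rule lacks an upper bound and so contradicts both the window and the summary limit in its own section, with no statement of which governs. Events dated wholly after last dose + 3 days can be counted in the treatment-emergent tables; whether they would be depends on which sentence the programmer follows.

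The number of events affected is unknown and probably small. The documents give no count of partial-date events or of off-drug onsets, and the per-event shift of 2.7 to 10 points rests on the planned or assumed arm sizes above. A reader might infer a bias against the arm with more early stops. That would need unequal stopping and affected events, and the documents give figures for neither. The internal contradiction does not depend on any of these assumptions.

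**What to change.** Reword the partial-date sentence in SAP 5.6.2 along these lines: an event with a partial or missing date is treatment-emergent unless (a) the partial onset date or the resolution date shows that it began before first administration, or (b) the known parts of the onset date show that it began after last dose + 3 days. Dates compatible with onset inside the window remain treatment-emergent.

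Add that the onset date imputed under SAP 5.1.4 is used to apply the summary limit. An event with a completely missing onset date has no imputed value, so say that it stays in the summaries unless exception (a) applies. State also that the 30-day SAE table keeps its own window.

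The cost is a clause and a short clarification in the SAP, and one derivation line, before database lock. No data collection changes and no ambiguous event is lost.

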5.6.3. Additional Safety Assessments

5.6.3.1. Clinical Laboratory Tests

Clinical laboratory tests will be displayed for the participants included in the safety analysis set and will be presented by study treatment for the entire study period. Local laboratory data will be included in listings and used only to find marked abnormalities.

The laboratory tests are summarized in table below:

Laboratory Assessments	Variables
Hematology	Hemoglobin Hematocrit Erythrocyte count Platelet count Leukocyte count with differential: Neutrophils Lymphocytes Monocytes Eosinophils Basophils
Clinical Chemistry	Alanine aminotransferase Aspartate aminotransferase Alkaline phosphatase Total and direct bilirubin Creatinine Sodium, potassium Serum albumin Glomerular filtration rate, using the Modification of Diet in Renal Disease formula Thyroid hormones: Free and total triiodothyronine (T3) Free and total thyroxine (T4) Thyroid stimulating hormone (TSH)
Other Tests	A serum pregnancy test for women of childbearing potential will be performed at Screening. Urine pregnancy tests will be performed at randomization and monthly thereafter. Urine pregnancy tests are either performed on-site during a scheduled visit or at home with the pregnancy test validated kit provided by the site. The results of the urine pregnancy tests will not be collected in the eCRF. Results of pregnancy tests will be documented in the participant's records (pregnancy test card). The date of the urine pregnancy test reported on the pregnancy card will be collected in the eCRF. Additional serum or urine pregnancy tests may be performed, if pregnancy is suspected during the study, as determined necessary by the investigator or required by local regulation, to establish the absence of pregnancy at any time during the participation in the study. NT-proBNP will be analyzed as part of the efficacy assessments.

Descriptive statistics (including change from baseline) will be presented for all chemistry and hematology laboratory tests at scheduled time points by treatment group.

An abnormality (abnormality based on criteria defined in tables in [Appendix 10](#)) will be attributed to the baseline and postbaseline values.

Postbaseline abnormalities will be compared with their corresponding baseline result:

- Treatment emergent (TE) will be concluded if the postbaseline value is worse than the baseline value.
- If the postbaseline value is above the upper limit and the baseline value is below the upper limit (eg, Normal or Low), then the postbaseline abnormality will be considered TE. The same applies to the postbaseline value being below the lower limit with the baseline value being above the lower limit (eg, Normal or High).
- If the baseline value is missing, a postbaseline abnormality will always be considered as TE.

Treatment-emergent marked laboratory abnormalities will be summarized for each laboratory variable for which marked abnormalities are defined providing their incidence and frequency.

In addition, the proportion of participants with the following treatment-emergent liver abnormalities will be summarized:

- ALT $\geq 3 \times$ upper limit of normal (ULN), ALT $\geq 5 \times$ ULN, ALT $\geq 8 \times$ ULN
- AST $\geq 3 \times$ ULN, AST $\geq 5 \times$ ULN, AST $\geq 8 \times$ ULN
- ALT or AST $\geq 3 \times$ ULN, ALT or AST $\geq 5 \times$ ULN, ALT or AST $\geq 8 \times$ ULN
- ALT or AST $\geq 3 \times$ ULN and concomitant (collected on the same day) bilirubin $\geq 2 \times$ ULN and both (ALT or AST and bilirubin) increased compared to baseline
- ALT or AST $\geq 3 \times$ ULN and bilirubin $\geq 2 \times$ ULN at any time and both (ALT or AST and bilirubin) increased compared to baseline

All laboratory data will be listed together with derived marked abnormality flag. A separate listing of marked abnormality laboratory values will be provided.

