|            | 
 
• Intervention-emergent AEs of special interest (eg, hypotension, anemia, hyperthyroidism).
 
• Change in vital signs (systolic and diastolic arterial blood pressure and pulse rate) and body weight from baseline to all assessed timepoints during the study.
 
• Intervention-emergent marked laboratory abnormalities.
 
• Change from baseline in forced vital capacity (FVC) and diffusing capacity of the lung for carbon monoxide (DLco).
 
• Change from baseline in supplemental oxygen rate.
 
• Change from baseline in arterial blood gas parameters.
 
 |

Refer to Section 8 for evaluations related to endpoints.

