5.6. Safety Analyses

All safety analyses will be based on the safety analysis set based on actual intervention received, unless otherwise specified. Analyses will be conducted for the entire study period only.

For all continuous safety variables, descriptive statistics by intervention group will include the N, mean, standard deviation, median, minimum, and maximum. Categorical variables will be summarized by intervention group using frequency counts and percentages.

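### SAP 5.6.3.1 flags laboratory abnormalities as treatment-emergent over the whole study with no limit tied to last dose, while treatment-emergent AEs stop 3 days after last dose

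*SAP*

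**What the plan says.** The protocol's safety endpoint (Section 3) is "Intervention-emergent marked laboratory abnormalities". SAP 5.6.3.1 grades laboratory values against the limits in Appendix 10 and then decides whether an abnormality is treatment-emergent:

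- General rule: "Treatment emergent (TE) will be concluded if the postbaseline value is worse than the baseline value". A value that crosses a limit not crossed at baseline also qualifies.
- No baseline: "If the baseline value is missing, a postbaseline abnormality will always be considered as TE".
- Period: laboratory data "will be presented by study treatment for the entire study period". Section 5.6 says the same of safety in general: "Analyses will be conducted for the entire study period only".
- Outputs: incidence of treatment-emergent marked abnormalities, and "the proportion of participants with the following treatment-emergent liver abnormalities will be summarized".

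For adverse events, SAP 5.6.2 uses a window linked to dosing: an AE from first administration "through the day of last dose plus 3 days is considered to be treatment emergent". One further table has a longer limit: "All SAEs up to 30 days after the last study treatment".

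For vital signs, SAP 5.6.3.2 confines the incidence table to the time during intervention but does not say when that time ends.

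**The concern.** The same label carries two meanings in one set of safety tables. For AEs, treatment-emergent means on drug or within 3 days of stopping. For laboratory values it means worse than baseline at any later point in the study. Consider a haemoglobin below 100 g/L (an Appendix 10 limit) that is worse than baseline and found eight weeks after the last tablet. It counts as treatment-emergent, yet an anaemia AE with onset that day does not.

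The liver rows are exposed in a further way. One row pairs a raised transaminase with a raised bilirubin at any time, so it could join an on-drug result to an off-drug result months later.

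Efficacy is now listed only and no hypothesis is tested (SAP 1 and 2), so the safety tables are the main by-arm outcome summaries left. If early stopping differs between arms, the share of off-drug values in those tables would differ as well.

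**Working it through.** The plan gives no figure to reproduce. The check compares passages and adds day arithmetic on target visit days.

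**1. The rules side by side**

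| Item | Start | End |
|---|---|---|
| Treatment-emergent AE (SAP 5.6.2) | first dose | last dose + 3 days |
| SAE table (SAP 5.6.2) | not restated | last dose + 30 days |
| Treatment-emergent laboratory abnormality (SAP 5.6.3.1) | after baseline | end of study |
| Treatment-emergent vital sign (SAP 5.6.3.2) | after baseline | during intervention, no day given |

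**2. Do off-drug samples exist?** Yes. Participants who stop early keep their visits until EOMOP (SAP 1.2; Protocol 1.3.2, footnote a). The haematology and chemistry row of Protocol 1.3.2 is marked at premature EOT, Weeks 20, 26 and 39, the six-monthly visit and unscheduled visits. It shows no mark at the safety call or at EOMOP; the table layout is partly broken. Local results also count towards marked abnormalities (SAP 5.6.3.1), and they are recorded for emergency hospitalisations (Protocol 10.2).

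**3. Day arithmetic.** Target days are 141 (Week 20), 183 (Week 26) and 274 (Week 39), each ±7. Assume a last dose on Day 85 (Week 12):

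- AE window closes: 85 + 3 = Day 88.
- SAE table closes: 85 + 30 = Day 115.
- Premature EOT due by: 85 + 7 = Day 92, which is 92 − 88 = 4 days past the AE limit.

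| Sample | Days after last dose | Days past AE limit | Days past SAE-table limit |
|---|---|---|---|
| Week 20 | 141 − 85 = 56 | 141 − 88 = 53 | 141 − 115 = 26 |
| Week 26 | 183 − 85 = 98 | 183 − 88 = 95 | 183 − 115 = 68 |
| Week 39 | 274 − 85 = 189 | 274 − 88 = 186 | 274 − 115 = 159 |

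Each of these samples, if it is taken before the premature EOMOP, stays eligible for the flag.

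**4. Does other text close the gap?** SAP Table 4 is titled for the double-blind treatment period, but its windows count from Day 1, have no end tied to last dose, and assign visits rather than emergent status. The output specifications cited in SAP 5.8.1 are not among the documents. They might hold an on-treatment rule, but that would not correct the SAP's wording.

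**The case against.** The strongest reply is that the whole-study period is a stated choice. SAP 5.6 and 5.6.3.1 both say so, and this SAP was simplified after the sponsor terminated the study. Protocol 9.5.2 likewise has AE summaries cover all events collected. This stands for the displays: showing every value is legitimate. It does not rescue the label, because the same protocol section ties intervention-emergent AEs to onset during the intervention period or to worsening of a pre-existing condition, and SAP 5.6.2 applies a 3-day limit.

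The reach is also narrow. It covers only participants who stopped early, stayed in follow-up and had a later abnormal sample that was worse than baseline or had no baseline. All laboratory data are listed with a marked-abnormality flag, so in a very small study a reader could find such values if the listings carry sample and dosing dates. Over-inclusion adds abnormalities rather than hiding them. All of this limits the size of the problem, though the by-arm tables remain mislabelled.

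Some stronger readings are tempting but unsupported:

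- *The laboratory window never ends.* It ends with the study; what is missing is a limit tied to last dose.
- *Laboratory samples are taken off drug at EOMOP itself.* The schedule row, as read, has no mark there.
- *Most post-stop samples are misclassified.* The Day 85 example would give four scheduled post-stop samples (premature EOT and Weeks 20, 26 and 39). That assumes full attendance and follow-up to Day 274, which the premature EOMOP may cut short.
- *The tables favour one arm.* No document gives stopping rates by arm.

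**Conclusion.** The inconsistency is real and should be corrected before the final tables are produced. As written, SAP 5.6.3.1 allows off-drug abnormalities to be reported as treatment-emergent, which does not match the endpoint's name or the SAP's own AE rule. This follows from the stated rule and is more than a missing detail.

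The practical effect is probably small. SAP 5.5.16 refers to a very limited number of participants, no hypothesis is tested, and only early stoppers with later abnormal samples are affected. How many such values exist cannot be derived from the documents, and neither can the direction of any between-arm effect. In so small a study, however, one participant can visibly move a by-arm percentage. The day counts rest on an assumed last dose at Week 12 and on attendance at the target days; they show what the rule permits and do not estimate what happened.

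**What to change.** In SAP 5.6.3.1, restrict the treatment-emergent flag to samples taken from first dose through one stated number of days after last dose. Apply it alike to scheduled, EOT, unscheduled and local samples. Two choices fit the documents:

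- **Last dose + 3 days.** This matches the AE rule and the on-treatment definition for the primary endpoint in Protocol 9.5.1.1. Premature-EOT samples taken 4 to 7 days after last dose would not be flagged.
- **Last dose + 7 days.** This includes the premature-EOT sample, which is due within 7 days. The SAP should then state that the window runs 7 − 3 = 4 days beyond the AE window.

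No document sets either figure for laboratory data, so the SAP should give its reason. An exception for the EOT sample alone is best avoided: it would treat an EOT sample 5 days after last dose differently from an unscheduled or local sample on the same day.

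Give the during-intervention condition in SAP 5.6.3.2 the same end. Keep later values in the whole-study displays and listings, marked off-treatment. Label any whole-study abnormality count *post-baseline*, not *treatment-emergent*.

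The cost is SAP wording, one date condition in the laboratory and vital-sign derivations, and an off-treatment marker. Slightly fewer values will be flagged, and early stoppers will be observed for less time, so crude incidence should be read against the exposure summaries in SAP 5.6.1. A footnote is needed where tables differ from those already produced for the DMC.
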